### **15.4 Specific Aim 3 Cost Effectiveness Analysis**

The analysis will be performed with an 18-month within trial time horizon and a longer simulated time horizon. The population considered in the CEA will be participants enrolled in the trial. The main outcome of interest is the incremental cost-effectiveness ratio (ICER) comparing the GLB+ to GLB group estimated by

$$ICER = \frac{Cost(GLB+) - Cost(GLB)}{Effect(GLB+) - Effect(GLB)} = \frac{\Delta Cost}{\Delta Effect}$$

where: the ratio  $\Delta Cost/\Delta Effect$  is interpreted as the incremental cost required to achieve one additional unit of health benefit, if the GLB+ extended intervention is used instead of the GLB extended intervention. Analyses will be performed from both a health care and a societal perspective, considering all direct medical and indirect costs as appropriate.

#### **15.4.1 Within-Trial CEA**

Utility scores collected in the trial will be combined with cost data to assess the within trial cost-utility of the treatment arms from both a health system (direct medical costs only) and societal perspective (direct and indirect medical costs).

#### **15.4.2 Simulation Modeling CEA**

Short-term outcomes (percent change in body weight, change in A1c, change in fasting glucose, etc.) measured for the GLB+ and GLB groups during the trial will be entered into a model derived from data from the DPP to predict progression to diabetes and reversion to normal glucose tolerance at 3 years. These data will then be used to simulate the 5- and 10-year cost-effectiveness of the intervention using the MMD, which allow us to consider all downstream costs including those of the intervention as well as those related to diabetes, its complications, and co-morbidities. All costs will be adjusted to the year 2017 using the U.S. Consumer Price Index. Future costs and health benefits will be discounted by 3% annually. Extensive sensitivity analyses will be conducted to assess the impact of variations in the parameters and assumptions on the outcomes.

Treatment Sequence	Initial Intervention	Subsequent Intervention	Subgroups in Design Figure
1	GLB core	GLB extend	A
2	GLB core	GLB+ extend	B
3	GLB+ core	GLB extend	C
4	GLB+ core	GLB+ extend	D

#### ***15.4. Analyses for Comparing Treatment Sequence on Weight Loss Maintenance (sub-aim)***

The analysis for this exploratory sub-aim will compare the 4 treatment sequences embedded in the adaptive design on percent weight change at 18-months. The primary comparison of interest is the GLB/GLB

intervention sequence to the GLB+/GLB+ intervention sequence across the 18-month timeframe. Whether the GLB+ intervention during the extended intervention phase is optimal following the core phase, especially for early non-responders, and whether the GLB+ intervention during the extended intervention phase is necessary to promote weight loss maintenance for those who initially achieved the 2.5% weight loss will be determined. The analysis will be based on an analysis of covariance model, using appropriate covariates (e.g., baseline weight), where we will compare the four groups using an F-test and then perform multiple comparisons using Tukey's HSD test.

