## **7.0 Research Design and Study Intervention**

Following baseline data collection, all participants will begin the 16-session core phase of the Group Lifestyle Balance (GLB) intervention. Percent weight change will be determined at the beginning of week 5, after 1 month of intervention. Those who achieve  $> 2.5\%$  weight loss will complete the remainder of the 12 GLB sessions. Those who achieve  $\leq 2.5\%$  weight loss will be stratified to the Group Lifestyle Balance Plus (GLB+) intervention (additional 12 sessions). A second round of data collection will

occur upon completion of the core intervention study phase, 4 months from baseline. Following this second data collection, participants will be matched into pairs based on gender and percent weight change at 4 months, and each person in a matched pair will be randomly assigned to treatment group for the extended intervention study phase. One person in each pair will receive either the standard GLB intervention or the augmented GLB+ intervention, and the second person in each pair will receive the alternate intervention. Following completion of the extended intervention study phase at 12 months, a third round of data collection will occur. A 6-month no contact phase will follow the extended intervention study phase to evaluate weight loss maintenance. The fourth and final round of data collection will occur upon completion of the 6-month no contact phase, 18 months from baseline.

The goals of both the GLB and GLB+ interventions include losing  $\geq 7\%$  of initial body weight and maintaining  $\geq 7\%$  weight loss through study end. The intervention group sessions will consist of 10-15 participants (to foster

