social support) and will be  $\sim 60$  minutes in length held during the noon hour or immediately after work to accommodate participants' work schedules. Those who miss a group session will be encouraged to attend a make-up session prior to the next regularly scheduled session. Approximately 15-20 cohorts of participants will complete the study, and several groups of participants will run concurrently for staffing purposes. Each participant will receive a copy of the weekly printed handouts, a fat and calorie counter, self-monitoring booklets, and a chart for recording body weight. Self-monitoring is a key strategy used during the intervention to promote self-regulation and goal attainment. Participants will be encouraged to self-monitor fat and calorie intake daily, to record their weekly minutes of PA, and to self-weigh (1 day/week in GLB). The monitoring records will be reviewed by the lifestyle coaches weekly with personalized feedback provided to participants.

Following completion of the 16-week core intervention phase, participants will enter the 8-month extended intervention phase. The extended phase will consist of 2 bimonthly group sessions followed by 7 monthly group sessions. The content presented will reinforce skills needed to achieve and maintain the behavioral goals. In addition, we will encourage continued goal attainment through individual goal setting, self-weighing, and social support. Participants will be encouraged to continue to self-monitor periodically (e.g., once/month) and to submit monitoring records for review. Finally, the 6-month maintenance phase of the study that follows the extended intervention phase will include no contact from program staff to assess sustainability of program outcomes.

When a participant does not attend a regularly scheduled group session, a make-up session will be scheduled for that person. The lifestyle coach will contact the participant to determine the reason for the missed session and to remind the individual to attend a

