## **8.0 Randomization**

Participants will be randomly assigned to treatment group following the 16-week core intervention phase. Participants will be matched, based on gender and percent weight change following the 4-month data collection visit. Each person in a matched pair will be randomly assigned to either the GLB or the GLB+ intervention for the extended and maintenance intervention phases. The biostatistician will create the randomization log and will be blinded to treatment group during the core intervention phase.

- **Process Responsibilities:** The Study Coordinator will maintain the master randomization list from the statistician. The Study Coordinator will be responsible for assigning randomization codes, notifying appropriate study staff that the participant has been randomized, and securely storing all randomization files.

The assigned and blinded randomization code, that is separate from study data, will be kept in a paper-based randomization log in a locked filing cabinet.

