### **15.3 Specific Aim 2 Analysis**

It is hypothesized that participants randomized to GLB+ will on average maintain  $\geq 7\%$  weight loss at 12- and 18-months compared to participants randomized to GLB, who are expected to maintain an average loss of 5%. A multiple regression model using the matched pair design described above will be employed in two ways: first, using the percent change at 12- and 18-months as repeated measures nested within matched pairs, and second, as absolute changes using baseline, 12-, and 18-month weights. Significant covariates chosen will be incorporated into these models.

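### The exploratory sequence ANCOVA (Section 15.4, sub-aim) does not fix the two matching variables as covariates; the randomised contrasts B−A and D−C need their own prespecified model, separate from A vs D (minor)

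*Combined protocol and SAP*

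**What the plan says.** Section 7.0 sets the randomisation: after the 4-month visit, "participants will be matched into pairs based on gender and percent weight change at 4 months", and one member of each pair goes to each extended-phase intervention. Section 8.0 repeats the two matching variables: "Participants will be matched, based on gender and percent weight change following the 4-month data collection visit". Core arm is not randomised. Sections 4.0 and 7.0 set it by week-5 weight response.

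The table in Section 15.4.2 defines four sequences (core/extended): A = GLB/GLB, B = GLB/GLB+, C = GLB+/GLB, D = GLB+/GLB+.

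For the main Aim 2 analysis, Section 15.3 carries the design forward: "A multiple regression model using the matched pair design described above will be employed in two ways". The exploratory sub-aim at the end of Section 15.4 does not. There, "The analysis will be based on an analysis of covariance model, using appropriate covariates (e.g., baseline weight" is all that is said about covariates, and the same model is to "compare the four groups using an F-test and then perform multiple comparisons using Tukey's HSD test". A vs D is called the primary comparison. The text also asks whether extended GLB+ "is optimal following the core phase, especially for early non-responders" (contrast D−C), and whether early responders need it (contrast B−A).

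**The concern.** Among the sequence comparisons, B−A and D−C are the ones between randomised groups within one core arm. Sex and 4-month change restrict that randomisation, and both are measured before it, so the model for these contrasts should include them. The plan leaves the choice open, and its one example is a weight taken before the core phase. Two things follow if only the example is used: information that predicts the 18-month outcome is left out, and the model standard error does not reflect the balance that pairing produced.

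The single four-group model is part of the difficulty. For B−A and D−C, 4-month change is a pre-randomisation covariate. For A vs D it is an outcome of the core phase, so adding it changes what that contrast estimates. One covariate set cannot serve both kinds of comparison. At stake are some precision and a prespecified choice in an exploratory analysis.

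**Working it through.** The documents give no sample size, SD or correlation for this analysis, so there is no plan figure to reproduce.

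**Inputs from the documents.** "The intervention group sessions will consist of 10-15 participants" and "Approximately 15-20 cohorts of participants will complete the study" (Section 7.0). If one cohort is one group, N lies between 15 × 10 = 150 and 20 × 15 = 300. Section 15.3 expects 7% against 5% loss, a difference of 2 points, stated for GLB+ vs GLB overall and not by sequence.

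**Assumptions.** N = 200; 18-month SD 7 points; half of participants in each core arm (50 per sequence); correlation of week 5 with month 4 of 0.6; correlation r of month 4 with month 18 from 0.3 to 0.7; week-5 response acts on month 18 only through month 4; baseline weight not prognostic; outcomes independent within group until step 4.

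**1. Model SE in closed form.** SE = s × √(2/50) = 0.2s, where s is the residual SD.
- Baseline weight only: the core-arm factor removes a share (0.6r)² × 2/π of the variance. At r = 0.6 this is 0.36² × 0.637 = 0.083, so s = 7√0.917 = 6.70 and SE = 1.34.
- With 4-month change: s = 7√(1 − r²) = 7 × 0.8 = 5.6 and SE = 1.12.

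**2. Simulation.** Pairs are formed on sex and sorted 4-month change and randomised within pair. Results for D−C are model SE (true SD). Reduction = 1 − (true SD adjusted ÷ true SD with baseline weight).

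| Pairing | r | Baseline weight only | 4-month change and sex | Reduction in true SD |
|---|---|---|---|---|
| Whole sample | 0.3 | 1.392 (1.356) | 1.341 (1.332) | 2% |
| Whole sample | 0.5 | 1.367 (1.295) | 1.219 (1.213) | 6% |
| Whole sample | 0.6 | 1.350 (1.232) | 1.126 (1.127) | 9% |
| Whole sample | 0.7 | 1.328 (1.177) | 1.005 (1.012) | 14% |
| Cohorts of 12 | 0.3 | 1.396 (1.367) | 1.346 (1.329) | 3% |
| Cohorts of 12 | 0.6 | 1.350 (1.303) | 1.127 (1.129) | 13% |
| Cohorts of 12 | 0.7 | 1.327 (1.265) | 1.006 (1.009) | 20% |
| Within core arm | 0.6 | 1.347 (1.154) | 1.121 (1.140) | 1% |

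At r = 0.6 the model SE falls by about 17% under every scheme (1 − 1.126/1.350 = 0.17). How much of this is real precision depends on the pairing, and the documents do not say across whom pairs are formed. With whole-sample pairing the baseline-weight SE overstates the true SD by 1.350/1.232 − 1 = 10%; within core arm, by 1.347/1.154 − 1 = 17%. The mean of D−C under the null is within 0.03 points of zero in all settings, so neither model is biased for it.

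**3. Power.** For 2 points at 0.025 per contrast with whole-sample pairing, power goes from about 20% to 22%, 27%, 31% and 39% at r = 0.3, 0.5, 0.6 and 0.7. It stays low, and these figures assume independent outcomes.

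**4. Clustering.** The extended phase is also delivered in group sessions (Section 7.0). With extended-phase groups of about 12, r = 0.6, whole-sample pairing and an assumed ICC, D−C gives model SE (true SD) and null rejection at nominal 2.5%:

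| ICC | Baseline weight only | 4-month change and sex, no group term |
|---|---|---|
| 0 | 1.35 (1.23), 1.2% | 1.12 (1.12), 2.3% |
| 0.02 | 1.35 (1.29), 1.8% | 1.12 (1.19), 3.4% |
| 0.05 | 1.34 (1.34), 2.4% | 1.12 (1.25), 4.4% |
| 0.05, groups also split by core arm | 1.34 (1.50), 5.0% | 1.12 (1.42), 7.6% |

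At r = 0.3 and ICC 0.05, both models reject too often (4.4% and 5.1%). The covariates still lower the true SD, for example by 1 − 1.25/1.34 = 7%, but without a group term the adjusted SE is too small.

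**5. Why A vs D must stay apart.** With no treatment effect, the core arms differ at month 18 by 0.6r × 7 × 2√(2/π). At r = 0.6 this is 0.36 × 7 × 1.596 = +4.0 points (simulated +4.06), from week-5 selection alone. With 4-month change in the model the simulated D−A is +0.02. That is not a cure. In a second simulation with other inputs (N = 300, correlation 0.58), core GLB+ improved 4-month change by 2 points and 18-month change by 1.8. The adjusted D−A was 0.03, so the core effect vanished with the selection. The baseline-weight model gave +1.22. Neither recovers a benefit of 1.8.

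**The case against.** The covariate list is only an example, so the matching variables are not excluded. The sub-aim is exploratory, B−A and D−C are unbiased without them, and Section 15.3 already uses the pairs for the main Aim 2 models. The size of the gain rests on an SD, a correlation and a pairing scheme that the documents do not give; at r = 0.3 it is negligible. Treating baseline weight as not prognostic also favours the adjusted model. All of this stands, and it is why the point is minor.

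Several stronger readings are tempting but not supported:
- **That the plan omits the matching variables or biases the randomised contrasts.** It leaves them open, and no bias appears.
- **That the unadjusted test errs safely and the covariates alone give correct standard errors.** This holds only if outcomes are independent within groups. The documents describe group delivery and give no ICC, so the direction is not established.
- **That 4-month change should simply be added to the existing model, which would also repair A vs D.** Step 5 shows that it would change that estimand and remove any core-phase effect.
- **That the Aim 2 models share the gap.** They use the matched pairs.

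A pair term, as in Aim 2, might seem the natural alternative. But core arm is not a matching variable. In the simulations about 40% to 48% of pairs straddle the two core arms, and these would carry little information on B−A or D−C. Covariates are the workable form.

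**Conclusion.** The concern holds as a minor point on the exploratory sub-aim. The plan does not fix the two variables that restrict the month-4 randomisation as covariates for B−A and D−C, and it places these contrasts in one model with the non-randomised A vs D. Relying on baseline weight alone costs precision, not validity of the estimates. Over the settings tried, the true SD of D−C would fall by 1% to 14% with whole-sample or within-core pairing, and by as much as 20% with pairing in cohorts of 12 at r = 0.7. The percentages do not depend on the assumed SD of 7, but they do depend on r and the pairing scheme. The unadjusted SE is too large if outcomes are independent within groups; at an ICC of 0.05 it can be about right or too small. Selection by week-5 response can by itself produce an A vs D difference of about 4 points at r = 0.6 under the same assumptions, so that contrast needs a label whichever covariates are used.

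**What to change.** In the sub-aim text of Section 15.4, specify two models.

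1. **For B−A and D−C:** ANCOVA of 18-month percent weight change on the four-sequence factor, with 4-month percent weight change, sex and baseline weight as fixed covariates. Standard errors allow for extended-phase intervention group, through a random group effect or cluster-robust errors, either with a small-sample correction (200/12 is only about 17 groups). State that these two contrasts are concluded from this model alone. Either keep the Tukey adjustment or name one adjustment for the two contrasts in advance, such as Holm at 0.05.
2. **For the four-group F-test, the Tukey table and A vs D:** the current ANCOVA with baseline weight and sex only, without 4-month change. Label A vs D as a non-randomised comparison, because core arm follows from week-5 response, and say that the first model is not a remedy for it.

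The cost is SAP wording, one extra exploratory model, and slightly wider standard errors from the group term. B−A and D−C will also appear in the Tukey table of the second model, so the text must say which result decides them. The covariates are already collected; extended-phase group membership must be kept in the analysis file.

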**Specific Aim 2:** Create matched pairs of participants based on sex and percent weight change at 4-months following the core intervention phase. Randomly assign each person in the pair to either the standard GLB intervention or to the augmented GLB+ intervention for the 8-month extended intervention phase. Evaluate the impact of the GLB+/GLB+ intervention sequence to the GLB/GLB intervention sequence at 12- and 18-month follow-up. One exploratory sub-aim will be to identify optimal treatment sequences embedded in the adaptive design on percent weight change at 18 months.

**Specific Aim 3:** Estimate the costs and cost-effectiveness of each intervention from a health system and societal perspective.

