### **4.0 Study Flow Diagram**

An overview of the general study processes is provided in Figure 1. In this trial, participants are not randomized to treatment group at baseline. Instead, all participants receive the first four weeks of the standard GLB intervention. During these first four weeks, participants learn basic skills such as self-monitoring, the calorie and fat content of food and beverages, and how to initiate a physical activity program such as brisk walking. Participants then remain in the standard GLB intervention if they achieve at least 2.5% weight loss at week 5. If participants do not achieve this level of weight loss, they will be stratified to the augmented GLB+ intervention at week 5. Participants will be randomized to treatment group following the core intervention phase (first 16 weeks) for the extended (8 months) and maintenance (6 months) intervention phases.

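### In the exploratory sequence sub-aim, the four-group F-test and all-pairs Tukey do not match the two randomised questions asked; pre-specify B vs A and D vs C instead

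*Combined protocol and SAP*

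**What the plan says.** Section 2.0, under Specific Aim 2, sets the goal: "One exploratory sub-aim will be to identify optimal treatment sequences embedded in the adaptive design on percent weight change at 18 months". The sub-aim section (headed 15.4, Analyses for Comparing Treatment Sequence) repeats the exploratory label: "The analysis for this exploratory sub-aim will compare the 4 treatment sequences embedded in the adaptive design on percent weight change at 18-months". The table just before it defines the sequences by core then extended phase: A is GLB/GLB, B is GLB/GLB+, C is GLB+/GLB and D is GLB+/GLB+.

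The method is an analysis of covariance "using appropriate covariates (e.g., baseline weight" being the only covariate named), "where we will compare the four groups using an F-test and then perform multiple comparisons using" Tukey's HSD. The section says "The primary comparison of interest is the GLB/GLB" sequence against GLB+/GLB+, which is A vs D. It then asks two further questions in words: whether extended GLB+ is best, particularly for early non-responders (D vs C), and whether it "is necessary to promote weight loss maintenance for those who initially achieved the 2.5% weight loss will be determined" (B vs A). Neither is set up as a planned contrast.

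On allocation, section 4.0 states: "If participants do not achieve this level of weight loss, they will be stratified to the augmented GLB+ intervention at week 5". Sections 7.0 and 8.0 randomise only the extended phase, within pairs matched on gender and 4-month percent weight change.

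**The concern.** No participant could have been assigned freely among A, B, C and D. Week-5 weight loss decides whether a person can reach A or B on the one hand, or C or D on the other. The choices that the design actually embeds are A or B for early responders and C or D for slow responders. A single test that all four means are equal, followed by all six pairs, treats the sequences as four exchangeable arms.

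Three things are at stake. A significant F-test may be read as evidence about extended GLB+ when it need not be. The comparison called primary may be read as a treatment effect when part of it is prognosis. And the two contrasts that do answer the stated questions carry a multiplicity allowance for four pairs that do not.

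**Working it through.** The plan gives no sample size, SD, power or alpha for this sub-aim, so there is no stated figure to reproduce.

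**Inputs**
- From the documents: four sequences; core arm set by week-5 loss (sections 4.0, 7.0); extended phase randomised (sections 7.0, 8.0); a 2-point difference in percent weight loss, 7% against 5%, borrowed from section 15.3.
- Assumed: family-wise two-sided 0.05 (0.05 is stated only for Aim 1); equal groups of n = 30-150; SD of 5-8 percentage points; no dropout.

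**Step 1: which pairs are randomised.** Four groups give 4 × 3 / 2 = 6 pairs. B-A and D-C hold core arm fixed and differ only in the randomised phase. A-C, A-D, B-C and B-D cross the week-5 split. The pooled contrast (B+D) against (A+C) is also randomised, but it is not a Tukey pair. Adjusting for week-5 loss would not rescue the crossing pairs: the allocation rule leaves no overlap in week-5 loss between A/B and C/D, so the adjustment would be extrapolation.

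**Step 2: what A vs D measures.** D - A = (D - C) + (C - A). The first term is randomised and the second is not. If extended GLB+ adds 2 points of loss and slow responders lie 2 points behind at 18 months, D - A = 2 - 2 = 0. Tukey would then reject this pair about 1% of the time (its per-pair level is about 0.0102), although GLB+ works.

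**Step 3: the F-test.** Let e be the extended GLB+ effect and g the 18-month gap between early and slow responders. The noncentrality is n(e² + g²)/SD² on 3 and 4n - 5 df. With e = 0, n = 50 per group:

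| Responder gap g | Rejection, SD 5 | Rejection, SD 7 |
|---|---|---|
| 0 | 5% | 5% |
| 1 | 18.9% | 11.6% |
| 2 | 64.4% | 35.9% |
| 3 | 95.5% | 71.1% |

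With e = 2, the share of noncentrality due to the gap is g²/(e² + g²): 0% at g = 0, 4/8 = 50% at g = 2, and 9/13 = 69% at g = 3.

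**Step 4: interval width.** Large-sample critical values are:
- Tukey, four groups: q(0.95; 4)/√2 = 2.569
- Bonferroni, two contrasts: z(1 - 0.05/4) = 2.241
- Bonferroni, three contrasts (A vs D kept): z(1 - 0.05/6) = 2.394

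The width ratios are 2.569/2.241 = 1.146 and 2.569/2.394 = 1.073.

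**Step 5: power for B-A or D-C.** If two-contrast power is 80%, the standardised shift is 2.241 + 0.842 = 3.083. Under Tukey, power is Φ(3.083 - 2.569) = 69.6%, a loss of 10.4 points. With three contrasts it is Φ(3.083 - 2.394) = 75.5%, so Tukey costs 5.9 points against that. Noncentral t results with a 2-point effect and 4n - 5 df:

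| n per group, SD | Two contrasts | Three contrasts | Tukey |
|---|---|---|---|
| 50, 5 | 40.0% | 34.1% | 28.0% |
| 100, 5 | 71.8% | 66.4% | 59.8% |
| 125, 5 | 81.9% | 77.6% | 72.0% |

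Over the whole assumed range, Tukey loses 4.6 to 13.1 points against two contrasts and 2.2 to 7.0 against three. In a simulation of 20,000 runs, requiring the F-test first added at most about 0.4 point, so the loss comes from Tukey's critical value and not from the F-test.

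**The case against.** The best defence is that nothing here is invalid. B vs A and D vs C are both among the Tukey pairs, so both are tested with family-wise control; Tukey is merely conservative for them. The section puts its questions within responder groups and nowhere says that the group with the highest mean will be called optimal. For a fixed responder share, ranking the embedded decision rules follows from the same two contrasts. The effect of extended GLB+ is also tested elsewhere, in the matched-pair model of section 15.3, so the trial does not rest on this F-test. And the sub-aim is exploratory.

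All of that stands, and it lowers the severity. It does not answer the structural point. The pair singled out as primary is one of the non-randomised ones, and the two randomised pairs are not designated as planned contrasts.

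A reader might go further and infer that the F-test mainly detects who responded by week 5, or that the best mean will almost surely belong to early responders. The documents do not support either. They give no 18-month responder gap, sample size or SD; the covariate list is open; and section 15.2 hypothesises no core-arm difference at 4 months. By Step 3, the gap outweighs a 2-point GLB+ effect only if it exceeds 2 points.

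**Conclusion.** The analysis does not match the questions. Only two of the six pairwise comparisons are randomised, and the named primary one, A vs D, is not among them. Rejection by the F-test is not evidence about extended GLB+, and a null A vs D is not evidence against it. These conclusions follow from the allocation rule; only the illustrative rejection rates depend on assumed values.

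The 15% in interval width rests only on large-sample critical values and a two-contrast family. The power cost is conditional: roughly 5-13 points against two Bonferroni contrasts and about 2-7 points if A vs D stays as a third, for a 2-point effect with n of 30-150 per group and SD of 5-8. A flat loss of 10 points might be inferred, but it holds only for the two-contrast family at 80% power, and the documents state neither. This is a cheap improvement of lower severity, because the sub-aim is exploratory.

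**What to change.** In the sub-aim section, replace the F-test and Tukey step with two pre-specified contrasts, B-A and D-C, at a joint two-sided 0.05. Use Bonferroni with simultaneous confidence intervals, or Holm if only the tests need adjusting.

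Define the optimal strategy as the better of A and B for early responders together with the better of C and D for slow responders. Report the mean under each of the four embedded rules (A+C, A+D, B+C, B+D) as p × mean(A or B) + (1 - p) × mean(C or D), with p the observed early-responder share.

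Report A vs D and the other three crossing pairs descriptively, labelled as non-randomised. Specific Aim 2 in section 2.0 also names the GLB+/GLB+ against GLB/GLB comparison, so its wording should be brought into line with whatever is decided.

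The cost is SAP wording; no new data are needed. The downside is that A vs D loses its formal test in this sub-aim. If the sponsor wants to keep that test, a three-contrast family (critical value 2.394) still improves on Tukey, but the result would need the same non-randomised label.
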